#### Table 14.3.4.4 Summary of Laboratory Results - Haematology - Worst Grade NCI-CTCAE Toxicity Shifts from Baseline (As Treated Population)

Freatment Group	CTCAE Worst Grade Post-Baseline value								
Baseline CTCAE Grade	Grade 0	Grade 1	Grade 2	Grade 3	Grade 4	Grade>=1	Grade>=3	Missing	Total [a]
Plitidepsin 2.5mg (N=XXX)									
Grade 0, n (%)	xxx (xxx.x)	xxx (xxx.x)	xxx (xxx.x)	xxx (xxx.x)	xxx (xxx.x)	xxx (xxx.x)	xxx (xxx.x)	xxx (xxx.x)	xxx (xxx.x
Grade 1, n (%)	xxx (xxx.x)	xxx (xxx.x)	xxx (xxx.x)	xxx (xxx.x)	xxx (xxx.x)	xxx (xxx.x)	xxx (xxx.x)	xxx (xxx.x)	xxx (xxx.y
Grade 2, n (%)	xxx (xxx.x)	xxx (xxx.x)	xxx (xxx.x)	xxx (xxx.x)	xxx (xxx.x)	xxx (xxx.x)	xxx (xxx.x)	xxx (xxx.x)	xxx (xxx.y
Grade 3, n (%)	xxx (xxx.x)	xxx (xxx.x)	xxx (xxx.x)	xxx (xxx.x)	xxx (xxx.x)	xxx (xxx.x)	xxx (xxx.x)	xxx (xxx.x)	XXX (XXX.)
Grade 4, n (%)	xxx (xxx.x)	xxx (xxx.x)	xxx (xxx.x)	xxx (xxx.x)	xxx (xxx.x)	xxx (xxx.x)	xxx (xxx.x)	xxx (xxx.x)	xxx (xxx.x
Missing, n (%)	xxx (xxx.x)	xxx (xxx.x)	xxx (xxx.x)	xxx (xxx.x)	xxx (xxx.x)	xxx (xxx.x)	xxx (xxx.x)	xxx (xxx.x)	xxx (xxx.x
Grade>=1, n (%)	xxx (xxx.x)	xxx (xxx.x)	xxx (xxx.x)	xxx (xxx.x)	xxx (xxx.x)	xxx (xxx.x)	xxx (xxx.x)	xxx (xxx.x)	xxx (xxx.x
Grade>=3, n (%)	xxx (xxx.x)	xxx (xxx.x)	xxx (xxx.x)	xxx (xxx.x)	xxx (xxx.x)	xxx (xxx.x)	xxx (xxx.x)	xxx (xxx.x)	xxx (xxx.x
Total, n (%)	xxx (xxx.x)	xxx (xxx.x)	xxx (xxx.x)	xxx (xxx.x)	xxx (xxx.x)	xxx (xxx.x)	xxx (xxx.x)	xxx (xxx.x)	XXX (XXX.X

N = number of patients in analysis set; n = number of patients with data available; % = percentages are calculated based on the Total number per row as the denominator.

[a] For Total column, percentages are calculated based on total number of patients with non-missing values at Baseline or Post-Baseline as the denominator.

Notes: The Baseline value is defined as last scheduled or unscheduled non-missing value from central Laboratory collected prior to the first dose of the first study drug administration.

Worst grade post-Baseline value is the highest post-Baseline grade recorded through the study.

'Low' relates to NCI-CTC grades for low results, 'High' relates to NCI-CTC grades for high results.

Grades were assigned using the Common Terminology Criteria for Adverse Events (CTCAE) Version 5.0. Reference: Listing 16.2.8.1.1

- Table template TLB006.
- Parameters are: Haemoglobin Low, Haemoglobin High, White Blood Cell Count Low, White Blood Cell Count High, Neutrophils Low, Eosinophils High, Lymphocytes Low, Lymphocytes High, and Platelet Count Low.

### Table 14.3.4.5 Summary of Laboratory Results - Serum Chemistry - Worst Grade NCI-CTCAE Toxicity Shifts from Baseline (As Treated Population)

reatment Group	CTCAE Worst Grade Post-Baseline value								
Baseline CTCAE Grade	Grade 0	Grade 1	Grade 2	Grade 3	Grade 4	Grade>=1	Grade>=3	Missing	Total [a]
litidepsin 2.5mg (N=XXX)									
Grade 0, n (%)	xxx (xxx.x)	xxx (xxx.x)	xxx (xxx.x)	xxx (xxx.x)	xxx (xxx.x)	xxx (xxx.x)	xxx (xxx.x)	xxx (xxx.x)	xxx (xxx.
Grade 1, n (%)	xxx (xxx.x)	xxx (xxx.x)	xxx (xxx.x)	xxx (xxx.x)	xxx (xxx.x)	xxx (xxx.x)	xxx (xxx.x)	xxx (xxx.x)	xxx (xxx.y
Grade 2, n (%)	xxx (xxx.x)	xxx (xxx.x)	xxx (xxx.x)	xxx (xxx.x)	xxx (xxx.x)	xxx (xxx.x)	xxx (xxx.x)	xxx (xxx.x)	XXX (XXX.)
Grade 3, n (%)	xxx (xxx.x)	xxx (xxx.x)	xxx (xxx.x)	xxx (xxx.x)	xxx (xxx.x)	xxx (xxx.x)	xxx (xxx.x)	xxx (xxx.x)	xxx (xxx.y
Grade 4, n (%)	xxx (xxx.x)	xxx (xxx.x)	xxx (xxx.x)	xxx (xxx.x)	xxx (xxx.x)	xxx (xxx.x)	xxx (xxx.x)	xxx (xxx.x)	xxx (xxx.y
Missing, n (%)	xxx (xxx.x)	xxx (xxx.x)	xxx (xxx.x)	xxx (xxx.x)	xxx (xxx.x)	xxx (xxx.x)	xxx (xxx.x)	xxx (xxx.x)	xxx (xxx.
Grade>=1, n (%)	xxx (xxx.x)	xxx (xxx.x)	xxx (xxx.x)	xxx (xxx.x)	xxx (xxx.x)	xxx (xxx.x)	xxx (xxx.x)	xxx (xxx.x)	xxx (xxx.y
Grade>=3, n (%)	xxx (xxx.x)	xxx (xxx.x)	xxx (xxx.x)	xxx (xxx.x)	xxx (xxx.x)	xxx (xxx.x)	xxx (xxx.x)	xxx (xxx.x)	xxx (xxx.y
Total, n (%)	xxx (xxx.x)	xxx (xxx.x)	xxx (xxx.x)	xxx (xxx.x)	xxx (xxx.x)	xxx (xxx.x)	xxx (xxx.x)	xxx (xxx.x)	XXX (XXX.)

N = number of patients in analysis set; n = number of patients with data available; % = percentages are calculated based on the Total number per row as the denominator.

[a] For Total column, percentages are calculated based on total number of patients with non-missing values at Baseline or Post-Baseline as the denominator.

Notes: The Baseline value is defined as last scheduled or unscheduled non-missing value from central Laboratory collected prior to the first dose of the first study drug administration.

Worst grade post-Baseline value is the highest post-Baseline grade recorded through the study.

'Low' relates to NCI-CTC grades for low results, 'High' relates to NCI-CTC grades for high results.

Grades were assigned using the Common Terminology Criteria for Adverse Events (CTCAE) Version 5.0.

Reference: Listing 16.2.8.1.2

- Table template TLB006.
- Parameters are: Alanine aminotransferase (ALT) High, Aspartate aminotransferase (AST) High, Alkaline phosphatase High, Gamma-Glutamyltransferase (GGT) High, Lactate dehydrogenase (LDH) High, Total Bilirubin High, Glucose (fasting) Low, Sodium Low, Sodium High, Potassium Low, Potassium High, Calcium Low, Calcium High, Magnesium Low, Magnesium High, Creatinine High, Albumin Low, Creatine Phosphokinase (CPK) High, Troponin T High, Amylase High, and Lipase High.

# 3.14 Vital Signs

#### Table 14.3.5.1 Summary of Vital Signs and Oxygen Saturation - Change from Baseline (As Treated Population)

Parameter (unit)									
	Plitidepsin 2.5mg (N=XXX)		Plitideps (N=Y	sin 1.5mg XXX)	Plitidep (N=2	psin Total Contro =XXX) (N=X		ol Arm KXX)	
Visit Statistic	Value at Visit	Change from Baseline	Value at Visit	Change from Baseline	Value at Visit	Change from Baseline	Value at Visit	Change from Baseline	
Baseline									
n Mean (SD) Median Q1, Q3 Min, Max	xxx xx.xx (xx.xxx) xx.xx xx.xx, xx.xx xx.x, xx.xx		XXX XX.XX (XX.XXX) XX.XX XX.XX, XX.XX XX.X, XX.X		XXX XX.XX (XX.XXX) XX.XX XX.XX, XX.XX XX.X, XX.X		XXX XX.XX (XX.XXX) XX.XX XX.XX, XX.XX XX.X, XX.X		
Day 2 – Pre-Infusion									
N Mean (SD) Median Q1, Q3 Min, Max	XXX XX.XX (XX.XXX) XX.XX XX.XX, XX.XX XX.X, XX.X	XXX XX.XX (XX.XXX) XX.XX XX.XX, XX.XX XX.X, XX.X	xxx xx.xx (xx.xxx) xx.xx xx.xx, xx.xx xx.x, xx.x	xxx xx.xx (xx.xxx) xx.xx xx.xx, xx.xx xx.x, xx.x	XXX XX.XX (XX.XXX) XX.XX XX.XX, XX.XX XX.X, XX.X	xxx xx.xx (xx.xxx) xx.xx xx.xx, xx.xx xx.x, xx.x	NA	NA	
Day 2 n Mean (SD) Median Q1, Q3 Min, Max etc.	NA	NA	NA	NA	NA	NA	xxx xx.xx (xx.xxx) xx.xx xx.xx xx.xx, xx.xx xx.x, xx.x	XXX XX.XX (XX.XXX) XX.XX XX.XX, XX.XX XX.X, XX.X	

N = number of patients in analysis set; n = number of patients with data available.

SD = Standard deviation; Q1 = 25th percentile; Q3 = 75th percentile; Min = Minimum; Max = Maximum; NA= Not Applicable.

Notes: The baseline value is defined as last scheduled or unscheduled non-missing value collected prior to the first dose of the first study drug administration. Reference: Listing 16.2.8.2.1

- Table template TVS002B.
- Parameters are: Systolic Blood Pressure (mmHg); Diastolic Blood Pressure (mmHg), Pulse rate (beats/min); Temperature (°C); Respiration Rate (breaths/min) and Oxygen Saturation at Room Air (%).
- Visits: Day 2 Pre-Infusion, Day 2, Day 3 Pre-Infusion, Day 3, Day 4, Day 5, Day 6, Day 7, Day 8, and Day 31.

• The displayed xxx do not reflect actual decimal precision. Please follow Section 2.11 for rounding rules.

#### Table 14.3.5.2 Summary of Vital Signs and Oxygen Saturation - Change during Plitidepsin Infusion (As Treated Population)

	Plitidepsin (N=X)	tidepsin 2.5mg Pli (N=XXX)		sin 1.5mg XXX)	Plitidepsin Total (N=XXX)	
Visit —	Change from the		(1)	Change from the	(1)	Change from the
Timepoint	Value at	Start of the	Value at	Start the of	Value at	Start the of
Statistic	Timepoint	Infusion	Timepoint	Infusion	Timepoint	Infusion
< <day x="">></day>						
Before the Start of the Plitidepsin Infusion						
n	XXX		XXX		XXX	
Mean (SD)	xx.xx (xx.xxx)		xx.xx (xx.xxx)		xx.xx (xx.xxx)	
Median	XX.XX		XX.XX		XX.XX	
Q1, Q3	xx.xx, xx.xx		xx.xx, xx.xx		xx.xx, xx.xx	
Min, Max	XX.X, XX.X		xx.x, xx.x		xx.x, xx.x	
Immediately at the End of the Plitidepsin Infu	sion					
n	XXX	XXX	XXX	XXX	XXX	XXX
Mean (SD)	xx.xx (xx.xxx)	xx.xx (xx.xxx)	xx.xx (xx.xxx)	xx.xx (xx.xxx)	xx.xx (xx.xxx)	xx.xx (xx.xxx)
Median	XX.XX	XX.XX	XX.XX	XX.XX	XX.XX	XX.XX
Q1, Q3	xx.xx, xx.xx	xx.xx, xx.xx	xx.xx, xx.xx	xx.xx, xx.xx	xx.xx, xx.xx	xx.xx, xx.xx
Min, Max	xx.x, xx.x	xx.x, xx.x	xx.x, xx.x	xx.x, xx.x	xx.x, xx.x	XX.X, XX.X
etc.						

N = number of patients in analysis set; n = number of patients with data available.

SD = Standard deviation; Q1 = 25th percentile; Q3 = 75th percentile; Min = Minimum; Max = Maximum.

Notes: The change from the start to the end of the plitidepsin infusion = immediately at end of the plitidepsin infusion value - before the start of the plitidepsin infusion value. Reference: Listing 16.2.8.2.1

- Table template TVS002B.
- Parameters are: Systolic Blood Pressure (mmHg); Diastolic Blood Pressure (mmHg), Pulse rate (beats/min); Temperature (°C); Respiration Rate (breaths/min) and Oxygen Saturation at Room Air (%).
- Visits: Day 1, Day 2 and Day 3.
- The displayed xxx do not reflect actual decimal precision. Please follow Section 2.11 for rounding rules.

### 3.15 Electrocardiograms (ECGs)

#### Table 14.3.6.1 Summary of 12-Lead Electrocardiogram (ECG) Parameters - Change from Baseline (As Treated Population)

Parameter (unit)								
	Plitidepsin 2.5mg (N=XXX)		Plitideps (N=X	sin 1.5mg XXX)	Plitidepsin Total (N=XXX)		Control Arm (N=XXX)	
Visit		Change from		Change from Change from				Change from
Statistic	Value at Visit	Baseline	Value at Visit	Baseline	Value at Visit	Baseline	Value at Visit	Baseline
Baseline								
n	XXX		XXX		XXX		XXX	
Mean (SD)	xx.xx (xx.xxx)		xx.xx (xx.xxx)		xx.xx (xx.xxx)		xx.xx (xx.xxx)	
Median	XX.XX		XX.XX		XX.XX		XX.XX	
Q1, Q3	xx.xx, xx.xx		xx.xx, xx.xx		xx.xx, xx.xx		xx.xx, xx.xx	
Min, Max	XX.X, XX.X		xx.x, xx.x		xx.x, xx.x		xx.x, xx.x	
< <day x="">></day>								
n	XXX	XXX	XXX	XXX	XXX	XXX	XXX	XXX
Mean (SD)	xx.xx (xx.xxx)	xx.xx (xx.xxx)	xx.xx (xx.xxx)	xx.xx (xx.xxx)	xx.xx (xx.xxx)	xx.xx (xx.xxx)	xx.xx (xx.xxx)	xx.xx (xx.xxx)
Median	XX.XX	XX.XX	XX.XX	XX.XX	XX.XX	XX.XX	XX.XX	XX.XX
Q1, Q3	xx.xx, xx.xx	xx.xx, xx.xx	xx.xx, xx.xx	xx.xx, xx.xx	xx.xx, xx.xx	xx.xx, xx.xx	xx.xx, xx.xx	xx.xx, xx.xx
Min, Max	xx.x, xx.x	xx.x, xx.x	xx.x, xx.x	xx.x, xx.x	xx.x, xx.x	xx.x, xx.x	xx.x, xx.x	xx.x, xx.x
etc.								

N = number of patients in analysis set; n = number of patients with data available.

SD = Standard deviation;Q1 = 25th percentile; Q3 = 75th percentile; Min = Minimum; Max = Maximum.

Notes: The Baseline value is defined as last scheduled or unscheduled non-missing value collected prior to the first dose of the first study drug administration. Reference: Listing 16.2.8.3.2

Programming notes (not part of the table):

- Table template TEG002B.
- Parameter is: Average QTcF interval (msec).

• Visits: Day 1 - Post-infusion, Day 3 - Post-infusion and Day 31.

• The displayed xxx do not reflect actual decimal precision. Please follow Section 2.11 for rounding rules.

xxx (xx.x)

xxx (xx.x)

xxx (xx.x)

xxx (xx.x)

Visit	Plitidepsin 2.5mg	Plitidepsin 1.5mg	Plitidepsin Total	Control Arm	
Parameter	(N=XXX)	(N=XXX)	(N=XXX)	(N=XXX)	
PCI Criterion	n (%)	n (%)	n (%)	n (%)	
< <day x="">> Patients at <<day x="">>, n1</day></day>	XXX	xxx	XXX	xxx	

xxx (xx.x)

xxx (xx.x)

#### Table 14.3.6.2 Potentially Clinically Important (PCI) Electrocardiogram (ECG) Results (As Treated Population)

N = number of patients in analysis set; n = number of patients with data available; n1 = number of patients with data available at visit; % = percentages are calculated based on n1 as the denominator;

xxx (xx.x)

xxx (xx.x)

QTcF = QT correction as calculated by Fridericia's formula.

Change from baseline > 30 msec

Notes: The Baseline value is defined as last scheduled or unscheduled non-missing value collected prior to the first dose of the first study drug administration. Reference: Listing 16.2.8.3.2

Programming notes (not part of the table):

Average QTcF Interval >500 msec

etc.

- Table template TEG005A.
- Visits: Day 1 Post-infusion, Day 3 Post-infusion and Day 31.
- Follow first footnote for calculation of percentages.

### 3.16 Functional Status - Barthel Index

V:-:4	Plitidepsin 2.5mg	Plitidepsin 1.5mg	Plitidepsin Total	Control Arm
VISIL Benthel Index Secure	$(\mathbf{N} = \mathbf{A}\mathbf{A}\mathbf{A})$	$(\mathbf{N} = \mathbf{A} \mathbf{A} \mathbf{A})$	$(\mathbf{N} = \mathbf{X} \mathbf{X} \mathbf{X})$	$(\mathbf{N} = \mathbf{A} \mathbf{A} \mathbf{A})$
Bartnei Index Score	h (%)	h (%)	h (%)	h (%)
Previous Month to COVID-19 Infection				
Patients with Previous Month to COVID-19 Infection	XXX	XXX	XXX	XXX
assessment, n1				
100%	xxx (xx.x)	xxx (xx.x)	xxx (xx.x)	xxx (xx.x)
95%	xxx (xx.x)	xxx (xx.x)	xxx (xx.x)	xxx (xx.x)
90%	xxx (xx.x)	xxx (xx.x)	xxx (xx.x)	xxx (xx.x)
85%	xxx (xx.x)	xxx (xx.x)	xxx (xx.x)	xxx (xx.x)
80%	xxx (xx.x)	xxx (xx.x)	xxx (xx.x)	xxx (xx.x)
<80%	xxx (xx.x)	xxx (xx.x)	xxx (xx.x)	xxx (xx.x)
Screening				
100%	xxx (xx.x)	xxx (xx.x)	xxx (xx.x)	xxx (xx.x)
95%	xxx (xx.x)	xxx (xx.x)	xxx (xx.x)	xxx (xx.x)
90%	xxx (xx.x)	xxx (xx.x)	xxx (xx.x)	xxx (xx.x)
85%	xxx (xx.x)	xxx (xx.x)	xxx (xx.x)	xxx (xx.x)
80%	xxx (xx.x)	xxx (xx.x)	xxx (xx.x)	xxx (xx.x)
<80%	xxx (xx.x)	xxx (xx.x)	xxx (xx.x)	xxx (xx.x)
<< Visit>>				
Patients at << Visit>>, n1	XXX	XXX	XXX	XXX
100%	xxx (xx.x)	xxx (xx.x)	xxx (xx.x)	xxx (xx.x)
95%	xxx (xx.x)	xxx (xx.x)	xxx (xx.x)	xxx (xx.x)
90%	xxx (xx.x)	xxx (xx.x)	xxx (xx.x)	xxx (xx.x)
85%	xxx (xx.x)	xxx (xx.x)	xxx (xx.x)	xxx (xx.x)
80%	xxx (xx.x)	xxx (xx.x)	xxx (xx.x)	xxx (xx.x)
<80%	xxx (xx.x)	xxx (xx.x)	xxx (xx.x)	xxx (xx.x)
etc.				

#### Table 14.3.7.1 Functional Status - Barthel Index (As Treated Population)

N = number of patients in analysis set; n = number of patients with data available; n1 = number of patients with data available at visit; % = percentages are calculated based on N for Screening or otherwise, on n1 as the denominator. Reference: Listing 16.2.6.2

- Table template TEG005A.
- Visits: Previous Month to COVID-19 Infection, Screening, Day 8, Day 15, Day 31 and At Discharge from Hospital.
- Follow first footnote for calculation of percentages.

# 3.17 Safety subgroup analyses

#### Table 14.3.8.1 Summary of TEAEs and Clinically Relevant Laboratory Tests - Worst Grade Post-Baseline - Subgroup Analysis (As Treated Population)

< <subgroup>></subgroup>								
	Plitidepsin (N=XX	2.5mg (X)	Plitidepsin (N=XX	1.5mg (X)	Plitidepsir (N=XX	n Total XX)	Control (N=X)	Arm XX)
	Grade >=1 or (>=ULN if not NCI-CTCAE		Grade >=1 or (>=ULN if not NCI-CTCAE		Grade >=1 or (>=ULN if not NCI-CTCAE		Grade >=1 or (>=ULN if not NCI-CTCAE	
Laboratory Abnormality/	grade)	Grade >=3	grade)	Grade >=3	grade)	Grade >=3	grade)	Grade >=3
TEAE	n (%)	n (%)	n (%)	n (%)	n (%)	n (%)	n (%)	n (%)
CTCAE: Anemia	xxx (xx.x)	xxx (xx.x)	xxx (xx.x)	xxx (xx.x)	xxx (xx.x)	xxx (xx.x)	xxx (xx.x)	xxx (xx.x)
CTCAE: Platelet count	xxx (xx.x)	xxx (xx.x)	xxx (xx.x)	xxx (xx.x)	xxx (xx.x)	xxx (xx.x)	xxx (xx.x)	xxx (xx.x)
decreased								
CTCAE: Neutrophil count	xxx (xx.x)	xxx (xx.x)	xxx (xx.x)	xxx (xx.x)	xxx (xx.x)	xxx (xx.x)	xxx (xx.x)	xxx (xx.x)
decreased	. .		.		, ,		.	
CTCAE: AP increased	xxx (xx.x)	xxx (xx.x)	xxx (xx.x)	xxx (xx.x)	xxx (xx.x)	xxx (xx.x)	xxx (xx.x)	xxx (xx.x)
CTCAE: Blood bilirubin	xxx (xx.x)	xxx (xx.x)	xxx (xx.x)	xxx (xx.x)	xxx (xx.x)	xxx (xx.x)	xxx (xx.x)	xxx (xx.x)
increased	( )	.				.	( )	, , , , , , , , , , , , , , , , , , ,
CTCAE: AST increased	XXX (XX.X)	xxx (xx.x)	XXX (XX.X)	XXX (XX.X)	XXX (XX.X)	XXX (XX.X)	XXX (XX.X)	xxx (xx.x)
CTCAE: ALT increased	xxx (xx.x)	xxx (xx.x)	xxx (xx.x)	xxx (xx.x)	xxx (xx.x)	xxx (xx.x)	xxx (xx.x)	xxx (xx.x)
CTCAE: CPK increased	xxx (xx.x)	xxx (xx.x)	xxx (xx.x)	xxx (xx.x)	xxx (xx.x)	xxx (xx.x)	xxx (xx.x)	xxx (xx.x)
CTCAE: LDH increased	xxx (xx.x)	NA	xxx (xx.x)	NA	xxx (xx.x)	NA	xxx (xx.x)	NA
Ferritin	xxx (xx.x)	NA	xxx (xx.x)	NA	xxx (xx.x)	NA	xxx (xx.x)	NA
D-dimer	xxx (xx.x)	NA	xxx (xx.x)	NA	xxx (xx.x)	NA	xxx (xx.x)	NA
TEAE: Nausea	xxx (xx.x)	xxx (xx.x)	xxx (xx.x)	xxx (xx.x)	xxx (xx.x)	xxx (xx.x)	xxx (xx.x)	xxx (xx.x)
TEAE: Vomiting	xxx (xx.x)	xxx (xx.x)	xxx (xx.x)	xxx (xx.x)	xxx (xx.x)	xxx (xx.x)	xxx (xx.x)	xxx (xx.x)
TEAE: Fatigue	xxx (xx.x)	xxx (xx.x)	xxx (xx.x)	xxx (xx.x)	xxx (xx.x)	xxx (xx.x)	xxx (xx.x)	xxx (xx.x)
TEAE: xxxxxxxxxx [a]	xxx (xx.x)	xxx (xx.x)	xxx (xx.x)	xxx (xx.x)	xxx (xx.x)	xxx (xx.x)	xxx (xx.x)	xxx (xx.x)

N = number of patients in analysis set within the subgroup; n = number of patients with data available; % = percentages are calculated based on N as the denominator.

[a] Grouped PT term presented in more than 5% of the patients within any treatment group.

Reference: Listing 16.2.7.1, 16.2.8.1.1, 16.2.8.1.2 and 16.2.8.1.4

- Use the PT = Nausea for TEAE: Nausea; the PT = Vomiting for TEAE: Vomiting and the PT = Fatigue for TEAE: Fatigue.
  - Add the grouped PT terms presented in more than 5% of the patients within any treatment group.
- Subgroups are:
  - Sex: female or male
  - Age at study entry: 18 to 39, 40 to 64,  $\geq 65$  years
  - Race: Asian, black, white, or other
  - Ethnic group: 'Hispanic or Latino' or 'Not Hispanic or Latino'
- Site location: Site XXX, Site XXX or Other Sites
- Previous COVID-19 vaccination status: 'Fully vaccinated', 'Non-fully vaccinated' or 'No vaccinated'
- SARS CoV 2 viral load (log10 copies/mL) at Day 1 before study drug administration: < 4, [4-7], > 7
- o Time between onset date of COVID-19 symptoms and initiation of study treatment: ≤5 days, 6 10 days, > 10 days
- Charlson Comorbidity Index (as derived using the eCRF data): 0 1 or > 1
- Geographical Region: Europe or Rest of the World
- Body mass index (kg/m2) at Screening:  $< 30 \text{ or } \ge 30$
- o Diabetes mellitus at Screening: 'None or diet controlled', 'Uncomplicated' or 'End-organ damage'
- Hypertension at Screening: Yes or No

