- Hypertension at Screening, defined as Hypertension (Standardised MedDRA Query [SMQ]) in the Medical History form: Yes or No
- Individual co-morbidities included in the Charlson Index: myocardial infarction (Yes or No), congestive heart failure (Yes or No), peripheral vascular disease (Yes or No), cerebrovascular disease (Yes or No), dementia (Yes or No), chronic obstructive pulmonary disease (Yes or No), connective tissue disease (Yes or No), peptic ulcer disease (Yes or No), liver disease ('None', 'Mild' or 'Moderate or Severe'), diabetes mellitus ('None or diet controlled', 'Uncomplicated' or 'End-organ damage'), hemiplegia (Yes or No), moderate or severe chronic kidney disease (Yes or No), solid tumor ('None', 'Localized' or 'Metastatic'), leukemia (Yes or No), lymphoma (Yes or No) or AIDS (Yes or No).
- ISARIC-4C mortality score: Low (0 3), Intermediate (4 8), High (9 14) or Very high (≥ 15)
- ISARIC-4C deterioration probability (%): `≤ 25', `(25 50]', or `> 50'
- Lactate dehydrogenase (LDH) at Baseline: ≤ ULN or > ULN

- CRP (mg/L) at Baseline: ≤ 100 or > 100
- D-dimer at Baseline: ≤ ULN or > ULN
- Ferritin at Baseline: ≤ ULN or > ULN
- Creatinine at Baseline: ≤ ULN or > ULN
- IL-6 at Baseline: ≤ Median or > Median value (at the analysis time cutoff may be updated based on distribution values if needed)
- IL-10 at Baseline: ≤ Median or > Median value (at the analysis time cutoff may be updated based on distribution values if needed)
- Lymphocytes count decreased at Baseline: 'Grade 0' or 'Grade  $\geq 1'$
- Neutrophils/lymphocytes ratio at Baseline:  $< 6 \text{ or } \ge 6$
- SARS-CoV-2 variant: Alpha, Beta, Gamma, Delta, Eta, Iota, Kappa, Lambda, Mu, or any potential new variant

The same covariates used for the primary efficacy endpoint analysis will be used for the subgroup analyses.

For ISARIC-4C mortality score and deterioration probability calculation:

- A Glasgow coma scale score of 15 is assumed for all the patients.
- Urea (mmol/L) will be calculated as blood urea nitrogen (mmol/L) \* 60 / 28.

Forest plots of the hazard ratios, and the 95% CI for the comparison of each dose of plitidepsin versus control arm will be presented by endpoint for all subgroups using the ITT population.

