### 7.7.2 Adverse Events

All AEs recorded on the eCRF will be coded using the MedDRA dictionary (Version 24 [or a later version if updated during the study]) and classified as TEAEs as follows:

• TEAEs are events with start date on or after the date of first dose of any study drug or events with start date prior to the date of first dose of any study drug whose severity worsens on or after the date of first dose of any study drug. If the event started on the date of first dose of the first study drug administration however it is ticked as the event started prior to first study drug administration on Day 1 in the eCRF, it will not be considered as a TEAE.

All AE data will be listed by treatment group with TEAE status flagged in the listing. In addition, listings of grade  $\geq$ 3 AEs, SAEs, AEs leading to discontinuation of any study drug, AEs resulting in death and AEs of special interest will be produced.

The AEs of special interest will be based on MedDRA version 24.0. The terms that determine the AEs of special interest are:

- For Rhabdomyolysis, Musculoskeletal disorders and CPK increases:
  - Rhabdomyolysis/Myopathy (SMQ)
  - Additional PTs: Back pain, Pain in extremity, Arthralgia
- For Hypersensitivity reactions:
  - Hypersensitivity (SMQ)
- For Cardiac events:
  - Cardiomyopathy (SMQ)
  - Cardiac arrhythmias (SMQ)
  - Cardiac failure (SMQ)
  - Additional PTs: Acute myocardial infarction, Cardiovascular insufficiency, Coronary artery disease, Myocardial infarction, Angina pectoris, Aortic valve incompetence, Aortic valve sclerosis, Atrial thrombosis, Cardiac disorder, Degenerative aortic valve disease, Left ventricular hypertrophy, Mitral valve incompetence, Myocardial ischaemia, Pericardial effusion, Pericarditis, Subendocardial ischaemia, Tricuspid valve incompetence, Blood creatine phosphokinase MB increased, Blood pressure increased, Cardiac murmur, Electrocardiogram QRS complex abnormal, Electrocardiogram ST segment abnormal, Electrocardiogram ST segment depression, Electrocardiogram ST-T change, Electrocardiogram ST-T segment abnormal, Electrocardiogram T wave abnormal, Electrocardiogram T wave amplitude decreased, Electrocardiogram T wave inversion, Oxygen saturation decreased, Pulse abnormal, Respiratory rate,

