For each laboratory analyte, the Baseline value will be defined as last scheduled or unscheduled non-missing value from central Laboratory collected prior to the first dose of the first study drug administration. Central Laboratory assessments carried out on the day of first study drug administration are considered to have taken place before the study drug administration, if the corresponding times have not been recorded.

For haematology and serum chemistry analytes, laboratory abnormalities from central Laboratory analytes will be graded according to NCI-CTCAE version 5.0. Shift tables presenting the number and percentage of patients cross-tabulating NCI CTC grade at baseline to the worst grade after baseline through the study (including results from unscheduled visits) will be provided by treatment group for the As Treated population. For analytes that have NCI-CTCAE gradings for both low and high values, low and high will be summarized separately. In the shifts of low values, any high values will be classified as normal and the worst low grade will be summarized. And in the shifts of high values, any low values will be classified as normal and the worst high grade will be summarized.

Haematology analyte	Low NCI CTC grade	High NCI CTC grade
Red Blood Cell Count	-	-
Haemoglobin	Х	Х
Haematocrit	-	-
White Blood Cell Count	Х	Х
Neutrophils (absolute)	Х	-
Eosinophils (absolute)	-	Х
Basophils (absolute)	-	-
Lymphocytes (absolute)	Х	Х
Monocytes (absolute)	-	-
Platelet count	Х	-

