### 7.7.7 Other Safety Variables

The number and percentage of patients per Barthel index category will be tabulated by visit, treatment group and overall plitidepsin for the As Treated population.

Subgroup analysis of TEAE and clinically relevant laboratory tests will be performed by treatment group and overall plitidepsin based on the following prognostic factors of medical interest for the As Treated population:

- Sex: female or male
- Age at study entry: '18 to 39', '40 to 64' or ' $\geq$ 65 years'
- Race: Asian, black, white, or other
- Ethnic group: 'Hispanic or Latino' or 'Not Hispanic or Latino'
- Site location: each study site with more than 1/6 out of the randomised patients (ie, >33 randomised patients for the futility analysis and >101 randomised patients for the final analysis) will be considered as a group and the remaining study sites, ie, those study sites with less than 1/6 out of the randomised patients will be pooled together as a one single group.
- Previous COVID-19 vaccination status: 'Fully vaccinated', 'Non-fully vaccinated' or 'No vaccinated'
- SARS-CoV-2 viral load (log10 copies/mL) at Day 1 before study drug administration: `< 4', [4-7] or `> 7'

- Time between onset date of COVID-19 symptoms and initiation of study treatment: `≤ 5 days', `6 10 days' or `> 10 days'
- Charlson Comorbidity index (as derived using the eCRF data): '0 1' or '> 1'
- Geographical Region: Europe or Rest of the World
- Body mass index (kg/m^2) at Screening: '< 30' or ' $\geq$  30'
- Diabetes mellitus at Screening: 'None or diet controlled', 'Uncomplicated' or 'End-organ damage'
- Hypertension at Screening (defined as Hypertension [SMQ] in the Medical History form): Yes or No

Clinically significant chest abnormalities detected by chest examinations (computed tomography scan or x-ray) are recorded in the eCRF as Medical History, Sign and Symptom or Adverse Events as appropriate and will be listed and summarized as such (See Sections 7.4.1 [Medical History], 7.4.3 [Signs and Symptoms] and 7.7.2 [Adverse Events]).

Chest imaging results (normal/abnormal) and details of abnormalities will be listed for each patient.

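### Laboratory rows of the safety subgroup table ignore baseline, which dilutes arm differences for LDH, ferritin and D-dimer in particular

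*SAP*

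**What the plan says.** SAP Section 7.7.7 introduces the table: "Subgroup analysis of TEAE and clinically relevant laboratory tests will be performed by treatment group and overall plitidepsin". It sets no baseline condition for the laboratory tests.

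The shell of Table 14.3.8.1, titled "Summary of TEAEs and Clinically Relevant Laboratory Tests - Worst Grade Post-Baseline - Subgroup Analysis (As Treated Population"), heads its first column "Grade >=1 or (>=ULN if not NCI-CTCAE" grade) and its second column Grade 3 or higher. Its footnote defines N as the patients of the analysis set within the subgroup and says that "percentages are calculated based on N as the denominator". The row "CTCAE: LDH increased" and the ferritin and D-dimer rows show NA in the Grade 3 column. The other laboratory rows (anaemia, platelets, neutrophils, alkaline phosphatase, bilirubin, AST, ALT, CPK) have both columns.

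The TEAE rows of the same table follow Section 7.7.2, which admits events that start on or after first dose, or earlier events "whose severity worsens on or after the date of first dose of any study drug".

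Elsewhere the SAP does use baseline. Section 7.7.3 plans shift tables "cross-tabulating NCI CTC grade at baseline to the worst grade after baseline through the study", for the whole As Treated population. Section 7.6.4 classifies LDH, ferritin and D-dimer at baseline, for example "D-dimer at Baseline: ≤ ULN or > ULN", but only to form efficacy subgroups.

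**The concern.** One table sets two kinds of count side by side without saying so. The TEAE rows show what began or worsened on treatment. The laboratory rows show who was abnormal at any time after baseline, including patients who entered abnormal.

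The table is there to show whether laboratory harm concentrates by age, comorbidity, body mass index and so on. In a hospitalised COVID-19 population some patients will enter with raised LDH, ferritin or D-dimer. For these three analytes the single threshold cannot separate a patient who was raised and stayed so from one whose value climbed on drug. Subgroups with more raised values at entry will show higher rates in every arm, and the difference between arms within them will be compressed.

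**Working it through.** The SAP states no figure for this table, so there is nothing to reproduce. The check is the counting rule plus an illustration on assumed rates.

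**Inputs**
- Counting rule and denominator: Table 14.3.8.1.
- b, the share of the subgroup already above ULN at baseline: not in the SAP. Assumed 60, 80 and 90%, with 30 and 50% added to show the range.
- p, the rate of new elevation among patients normal at baseline: assumed 30% on control and 50% on plitidepsin, a true difference of 20 points.
- s, the share of already raised patients who are raised at least once after baseline: assumed 100% in both arms. Appendix 4 schedules chemistry, immunology and coagulation on Day 2, one day after the Day 1 baseline, so few would escape the count.
- For LDH, which the table treats as graded, Grade 1 is taken to begin above ULN. The SAP does not print the grade limits.

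**Table as written**

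Printed rate = b × s + (1 − b) × p. With s equal in both arms, the arm difference = (1 − b) × (50 − 30) points.

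| b | Control | Plitidepsin | Difference |
|---|---|---|---|
| 30% | 0.30 + 0.70 × 0.30 = 51% | 0.30 + 0.70 × 0.50 = 65% | 14 points |
| 50% | 0.50 + 0.50 × 0.30 = 65% | 0.50 + 0.50 × 0.50 = 75% | 10 points |
| 60% | 0.60 + 0.40 × 0.30 = 72% | 0.60 + 0.40 × 0.50 = 80% | 8 points |
| 80% | 0.80 + 0.20 × 0.30 = 86% | 0.80 + 0.20 × 0.50 = 90% | 4 points |
| 90% | 0.90 + 0.10 × 0.30 = 93% | 0.90 + 0.10 × 0.50 = 95% | 2 points |

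The result does not depend on s = 100%. With s = 95% and b = 90%, the rates are 0.855 + 0.030 = 88.5% and 0.855 + 0.050 = 90.5%, again 2 points apart.

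**Patients already raised**

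Their rate is s in each arm. A further rise on drug adds nothing; the row responds only if the drug changes whether they return to normal at every later visit.

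**Which denominator repairs it**
- New elevations over all patients with baseline and post-baseline values: (1 − b) × p gives 12 vs 20%, 6 vs 10% and 3 vs 5% at b = 60, 80 and 90%. The differences are still 8, 4 and 2 points.
- New elevations over patients at or below ULN at baseline: 30 vs 50%, a 20-point difference at every b.

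Only the second removes the dilution.

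**Boundary**

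Table 14.3.8.1 counts values at or above ULN for ungraded analytes, whereas Section 7.6.4 calls a baseline value raised only above ULN. A ferritin or D-dimer value equal to ULN is therefore normal in one place and abnormal in the other.

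**The case against.** A reader might infer that the rates saturate and that a drug effect disappears. The documents do not support that. The SAP gives no baseline prevalence, and the ULN splits in Section 7.6.4 define categories without saying how many patients fall in each. The effect is diluted by 1 − b and comes close to zero only when b is about 90% or more; 8 points at 60% is not disappearance.

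Nor are all laboratory rows equally affected. A patient moving from Grade 1 to Grade 3 in ALT or CPK appears in the Grade 3 column. The difficulty is acute for three rows only.

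The report as a whole does look at baseline. LDH is in shift Table 14.3.4.5, D-dimer value and change from baseline are in Table 14.3.4.3, and ferritin percent change relative to ULN is in Table 14.2.3.20, with plots in Figures 14.2.2.9.1 and 14.2.2.9.2. The control arm stands in the same table, so a high background rate is visible, and the title says that worst post-baseline grade is what is counted. The table is descriptive.

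All of this stands, and it limits the point to a modest one. What it leaves untouched is that none of these baseline-aware displays is produced by subgroup, and that a visible background rate does not undo the compression of the arm difference. Coverage of LDH is also thinner than it looks: Section 7.7.3 lists it as a serum chemistry analyte, but the parameter list of change-from-baseline Table 14.3.4.2 omits it.

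**Conclusion.** The point holds as a minor weakness of one descriptive table. The laboratory rows of Table 14.3.8.1 carry no baseline condition while the TEAE rows do. For LDH, ferritin and D-dimer the single threshold hides worsening in patients already raised, and it multiplies a difference among patients normal at baseline by 1 − b.

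The rule and the factor follow from the document. The printed sizes (20 points becoming 8, 4 or 2) rest on assumed baseline shares and onset rates, and on equal persistence of abnormality across arms. It would go too far to say that a drug effect is lost: it is diluted in this table and remains visible, for the whole population, in others. What is missing is a baseline-aware laboratory view by subgroup.

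**What to change.** Add the following to Table 14.3.8.1 and keep the present columns as a secondary display.

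- Graded rows: the number and percentage of patients whose worst post-baseline grade exceeds their baseline grade, among patients with both values.
- LDH, ferritin and D-dimer: new elevation, with patients at or below ULN at baseline and with a post-baseline value as the denominator.
- The same three analytes, patients already above ULN: a separate row counting worsening by a multiple of baseline that is stated before the output is run.
- One convention at the limit, so that the table and Section 7.6.4 treat a value equal to ULN alike.
- LDH in the parameter list of Table 14.3.4.2.
- At the least, a footnote that the laboratory rows are not treatment-emergent.

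The cost is small. Baseline and worst grades are already derived for the shift tables, and ECG Table 14.3.6.2 already uses patients with data as its denominator. Database lock has passed, so this would be a supplementary post-hoc display; Section 1 of the SAP Addendum allows tables to be added.

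The price is smaller denominators. Even with the planned 203 per arm, restriction to patients normal at baseline leaves about 81, 41 or 20 per arm at b = 60, 80 or 90% (203 × 0.40, 0.20, 0.10) before any subgrouping. Section 8 records that recruitment stopped before 33% of events, so actual cells will be smaller, and counts should be printed beside every percentage.
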